7.6.2.4. Efficacy Event Endpoints

Analysis population(s): FAS

Analysis parameter(s): Event categories 1 through 14 below

1. Composite endpoint of end-stage renal disease (ESRD) onset, doubling of serum creatinine, renal death, and cardiovascular (CV) death
2. Composite endpoint of CV death and hospitalized congestive heart failure
3. Composite endpoint of CV death, non-fatal myocardial infarction, and non-fatal stroke
4. Hospitalized congestive heart failure

5. Composite renal endpoint of end-stage renal disease (ESRD), doubling of serum creatinine, and renal death
6. CV death
7. All-cause death
8. The CV composite endpoint of CV death, non-fatal myocardial infarction, non-fatal stroke, hospitalized congestive heart failure, and hospitalized unstable angina
9. ESRD
10. Doubling of serum creatinine
11. Renal death
12. Non-fatal myocardial infarction
13. Non-fatal stroke
14. Hospitalized unstable angina

Analysis method:

For the data in “6.4 Handling of Event Endpoint Data,” for each of the endpoint event categories 1 through 14, the number and proportion of subjects experiencing the events in question, as well as the event incidence per 1000 person-years, will be calculated for each treatment group. Kaplan-Meier curves will be presented for each treatment group for endpoint event categories 1 through 8.

Endpoint event categories 1 through 14 will be analyzed using a stratified Cox proportional hazard model in which the baseline hazard is stratified based on the eGFR on the first day of the run-in period (≥ 30 mL/min/1.73 m² and < 45 mL/min/1.73 m², ≥ 45 mL/min/1.73 m² and < 60 mL/min/1.73 m², ≥ 60 mL/min/1.73 m² and < 90 mL/min/1.73 m²), with treatment group included as a factor, and the hazard ratios, 95% confidence intervals, and P values will be presented.

For the endpoint event categories 1 through 14, the number and proportion of subjects experiencing the events in question, as well as the hazard ratios and 95% confidence intervals thereof, will be presented in forest plots for each treatment group.

Listings

Analysis population(s): Randomized subjects

7.6.3. Issues in Statistical Analyses

7.6.3.1. Adjustments for Covariates

An analysis using a logistic regression model was performed in “7.6.1.2. Secondary Analysis” and “7.6.1.3. Other Analyses,” and the log-transformed urine ACR level (first morning void urine) on the first day of the treatment period was used as a covariate.

An analysis using a mixed model for repeated measures was performed in “7.6.2.2. Percent Changes

in the Urine ACR (First Morning Void Urine) and Fasted Urine Glucose/Creatinine Ratio,” and the log-transformed value of the analysis parameter on the first day of the treatment period and the interaction between the assessment time point and the log-transformed value of the analysis parameter on the first day of the treatment period were used as covariates.

An analysis using a mixed model for repeated measures was performed in “7.6.2.3. The Change in eGFR, HbA1c, Fasting Blood Glucose, Blood Pressure (Systolic Blood Pressure, Diastolic Blood Pressure), Lipids (HDL-C, Fasting Neutral Lipids), and Body Weight, and the Percent Change in eGFR, Lipids (HDL-C, Fasting Neutral Lipids), and Body Weight,” and the value of the analysis parameter on the first day of the treatment period and the interaction between the assessment time point and the value of the analysis parameter on the first day of the treatment period were used as covariates.

7.6.3.2. Handling of Dropouts or Missing Data

See “6. Data Handling.”

7.6.3.3. Interim Analyses and Data Monitoring

Not applicable

7.6.3.4. Multicenter Studies

This study is not a multicenter study.

7.6.3.5. Multiple Comparison/Multiplicity

Not applicable

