9.2.3 Efficacy Evaluation

9.2.3.1 eGFR

Blood samples will be collected at the following visits, and the eGFR measured at a central laboratory: the first day of the run-in period; the first day of the treatment period; Weeks 4, 8, 12, 16, 20, 24, 28, 32, 36, 40, 44, 48, 52, 64, 76, 88, and 104 of the treatment period (or at treatment period discontinuation); and Week 4 of the follow-up observation period.

The blood samples will be collected at the study sites, and the measurements and calculations will be performed at the central laboratory. The collection of the specimens will be performed by the central laboratory. The test result printouts that are provided by the central laboratory will be retained by the study sites.

The eGFR will be calculated using the following formula, which is the formula for estimating the GFR in Japanese:

$$\text{eGFR (mL/min/1.73m}^2\text{)} = 194 \times \text{Serum creatinine}^{-1.094} \times \text{Age}^{*0.287} \text{ (females: } \times 0.739\text{)}$$

*Age: Subject's biological age in years

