7.1.3. Significance Level and Confidence Coefficient

The tests will be all two-sided, with a significance level of 5%. The confidence intervals will be two-sided, and the confidence coefficient will be 95%.

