For the data described in “6.2.3. Tabulation of Endpoints Other Than the eGFR and Urine ACR at Each Assessment Time Point” and “6.2.4. Tabulation of the Urine ACR Endpoints at Each Assessment Time Point,” the mean changes in the log-transformed values of each analysis parameter at each assessment time point from Week 4 to Week 104 will be analyzed in a mixed model for repeated measures using a restricted maximum likelihood (REML) approach, with treatment group, assessment time point, treatment group—assessment time point interaction, and the stratification factor of the eGFR on the first day of the run-in period (≥ 30 and < 45 , ≥ 45 and < 60 , ≥ 60 and < 90) as factors, and the log-transformed values of the assessment parameters on the first day of the treatment period and the interactions between the assessment time points and the log-transformed values of the assessment parameters on the first day of the treatment period as covariates. For each treatment group at each assessment time point, the LS mean and standard error, 95% confidence interval, difference between the groups (the TA-7284 group minus the placebo group) in the LS mean, and the standard error and 95% confidence interval thereof, will be calculated. Additionally, the LS means and 95% confidence intervals of the changes in the log-transformed values will be back-transformed, and the geometric LS means and 95% confidence intervals of the ratios of each analysis parameter will be presented. The values obtained from the following formula will be presented as the percent change from baseline: (geometric LS mean of the ratio in the analysis parameter – 1) $\times 100$. Also, the differences between the groups (the TA-7284 group minus the placebo group) in the LS means, and the 95% confidence intervals thereof, will be back-transformed, and the ratios of the geometric LS means of the ratios of the analysis parameters, and the 95% confidence intervals and P values, will be presented. The percent changes relative to placebo [(ratio of the geometric LS means of the ratio of each analysis parameter – 1) $\times 100$] will also be presented.

The Kenward-Roger method will be used to adjust the degrees of freedom, and an unstructured covariance structure will be used for within-subject error modeling.

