Endpoints Other Than the eGFR and Urine ACR at Each Assessment Time Point,” each of the mean changes at each assessment time point from Week 4 to Week 104 in the eGFR, HbA1c, fasting glucose, blood pressure (systolic blood pressure, diastolic blood pressure), lipids (HDL-C, fasting neutral lipids), and body weight, and the mean percent changes at each assessment time point from Week 4 to Week 104 in the eGFR, lipids (HDL-C, fasting neutral lipids), and body weight will be analyzed in a mixed model for repeated measures using a restricted maximum likelihood (REML) approach, with treatment group, assessment time point, treatment group—assessment time point interaction, and the stratification factor of the eGFR on the first day of the run-in period (≥ 30 and < 45 , ≥ 45 and < 60 , ≥ 60 and < 90) as factors, and the values of the assessment parameters on the first day of the treatment period and the interactions between the assessment time points and the values of the assessment parameters on the first day of the treatment period as covariates. The LS means and standard errors at each measurement time point for each treatment group will be presented. The differences between the groups in the LS mean (the TA-7284 group minus the placebo group) and the 95% confidence intervals and P values will also be presented. In addition, time profiles will be prepared for each treatment group for each of the mean change and the mean percent change, with the LS means and standard errors, calculated based on MMRM, along the y-axis and each measurement time point up through Week 104 along the x-axis.

The Kenward-Roger method will be used to adjust the degrees of freedom, and an unstructured covariance structure will be used for within-subject error modeling.

However, in within-subject error modeling, if the model fails to converge when using an unstructured covariance matrix, the covariance matrix will be changed according to the following procedure, and the first covariance matrix with successful convergence will be used to perform the analysis.

Heterogeneous Toeplitz (TOEPH) → Heterogeneous AR(1) (ARH(1)) → Heterogeneous CS (CSH) → Toeplitz (TOEP) → First-order autoregressive (AR(1)) → Compound symmetry (CS)

Listings

Analysis population(s): Randomized subjects

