7.6.3.8. Analyses of Subgroups

The following subgroup analyses will be performed for the analysis described in 7.6.1.1.

Analysis population(s): FAS

Subgroups: Sex (male, female), age (< 65 years, \geq 65 years), disease duration of type2 diabetes (< median in years, \geq median in years), BMI (< 30, \geq 30), HbA1c on the first day of the treatment period (< 8, \geq 8), eGFR on the first day of the run-in period (\geq 30 and < 45, \geq 45

and < 60 , ≥ 60 and < 90), mean of the eGFR on the first day of the run-in period and that on the first day of the treatment period (< 45 , ≥ 45 and < 60 , ≥ 60), urine ACR on the first day of the treatment period (≤ 1000 , > 1000), systolic blood pressure on the first day of the treatment period (\leq median value, $>$ median value)

Analysis parameter(s): Proportions of subjects with declines of 30% and 40% in the eGFR at Week 104 of the treatment period

Analysis method:

In accordance with “6.2.2. Tabulation of the eGFR at Each Assessment Time Point When Imputing Data Outside the Allowable Time Window,” a dataset will be prepared using [REDACTED] by subgroup. The estimates and variances for this dataset will be combined using Rubin’s rule, and the proportions of subjects with declines of 30% and 40% in the eGFR at Week 104 of the treatment period, the point estimates for the differences between the groups (placebo group minus TA-7284 group), and the 95% confidence intervals based on the Farrington-Manning method, will be calculated for each treatment group. These figures, along with the numbers and proportions of subjects in each of these subgroups, will be presented in forest plots.

The following subgroup analyses will be performed for the analysis described in 7.6.2.2 and 7.6.2.3.

Analysis population(s): FAS

Subgroups: eGFR on the first day of the run-in period (≥ 30 and < 45 , ≥ 45 and < 60 , ≥ 60 and < 90)

Analysis parameter(s): Urine ACR (first morning void urine), eGFR, HbA1c, blood pressure (systolic blood pressure, diastolic blood pressure)

Analysis method:

Urine ACR (First Morning Void Urine)

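### The SAP sets a 5% level for all tests and calls multiplicity not applicable, yet plans about 505 secondary and eGFR-band P values that it neither orders nor labels as nominal

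*SAP*

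**What the plan says.** SAP 7.1.3 reads "The tests will be all two-sided, with a significance level of 5" percent, with no restriction to any endpoint. SAP 7.6.3.5, headed "Multiple Comparison/Multiplicity", consists of the reply that it is not applicable.

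Between-arm P values are then requested in four places:

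- SAP 7.6.2.2, for urine ACR and the fasting urine glucose/creatinine ratio at each visit from Week 4 to Week 104: "and the 95% confidence intervals and P values, will be presented".
- SAP 7.6.2.3, for eight changes and four percent changes at each visit: "and the 95% confidence intervals and P values will also be presented".
- SAP 7.6.2.4, for 14 event categories in stratified Cox models: "the hazard ratios, 95% confidence intervals, and P values will be presented".
- SAP 7.6.3.8, which repeats part of this within three bands of run-in eGFR: "The following subgroup analyses will be performed for the analysis described in 7.6.2.2 and 7.6.2.3". P values are again requested there for ACR, eGFR, HbA1c and blood pressure.

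The primary analysis (Protocol 13.3.2, SAP 7.6.1.1) is given as a difference in proportions with a Farrington-Manning 95% interval. The visible text mentions no P value for it. Protocol 13.3 sets 95% intervals and no significance level, and for event endpoints Protocol 13.3.2 plans only incidences and Kaplan-Meier plots. The 5% level and the Cox models appear first in the SAP, and SAP section 9 lists neither as a change from the protocol.

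**The concern.** In the visible text, the 5% rule acts only on analyses for which multiplicity is left unaddressed. The one comparison with a clear claim to error control is reported by interval. The many comparisons without any control are the ones reported by P value. There is no testing order, no allocation of alpha, no designated visit for the repeated-measures endpoints, and no remark that these P values are descriptive.

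Read literally, 7.1.3 allows any of them below 0.05 to be called significant. Protocol section 1(4) says that the trial is meant to support a Japanese indication for overt nephropathy. With up to 17 visits per endpoint and three eGFR bands, isolated small P values are easy to find. The plan should say in advance what weight they carry.

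**Working it through.** The SAP states no number of tests, so there is no figure of its own to reproduce. The count below takes only analyses for which the SAP says P values will be presented, as parameters × scheduled post-baseline visits × bands.

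**Visits (Protocol 9.2.3 and 9.2.4)**

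- eGFR, HbA1c, fasting glucose, lipids and blood pressure: "Weeks 4, 8, 12, 16, 20, 24, 28, 32, 36, 40, 44, 48, 52, 64, 76, 88, and 104 of the treatment period", which is 17 visits.
- Urine ACR and urine glucose/creatinine: 10 visits (Weeks 4, 8, 12, 24, 36, 52, 64, 76, 88, 104).
- Body weight: 8 visits (Weeks 12, 24, 36, 52, 64, 76, 88, 104).

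**Count**

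| Source | Formula | P values |
|---|---|---|
| 7.6.2.2, ACR and urine glucose/creatinine | 2 × 10 | 20 |
| 7.6.2.3, changes (7 parameters at 17 visits, weight at 8) | 7 × 17 + 8 | 127 |
| 7.6.2.3, percent changes (eGFR, HDL-C and neutral lipids at 17, weight at 8) | 3 × 17 + 8 | 59 |
| Full-FAS repeated-measures subtotal | 20 + 127 + 59 | 206 |
| 7.6.2.4, Cox models | 14 | 14 |
| 7.6.3.8, three eGFR bands (ACR at 10; four changes and eGFR percent change at 17) | 3 × (10 + 5 × 17) | 285 |
| Total | 206 + 14 + 285 | 505 |

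**Expected number below 0.05 under a global null.** This is 505 × 0.05 = 25.25. An expectation is additive whatever the correlation. By symmetry about half, 12.6, would favour each arm. The full-FAS analyses alone give (206 + 14) × 0.05 = 11.0.

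**Leaving out measures on which the documents expect an effect.** Protocol section 1 describes the drug as raising urinary glucose excretion and lowering blood glucose, causing an early fall in eGFR, and reducing albuminuria. The P values on those measures, full FAS plus bands, are:

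- HbA1c: 17 + 3 × 17 = 68
- fasting glucose: 17
- urine glucose/creatinine: 10
- ACR: 10 + 3 × 10 = 40
- eGFR, change and percent change: 34 + 3 × 34 = 136

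These sum to 271, leaving 505 − 271 = 234. As a check, the remainder is blood pressure 34 + 3 × 34 = 136, lipids 4 × 17 = 68, weight 16 and Cox 14, which sum to 234. If there were no effect on any of these, 234 × 0.05 = 11.7 would be expected below 0.05, about 5.9 in each direction.

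**Sensitivity to the Cox models.** Some may not be estimable if events are few. Dropping all 14 gives 491 × 0.05 = 24.55 in total, and 220 × 0.05 = 11.0 in the reduced set.

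The count omits comparisons given by interval only: the 30% and 40% decline analyses, their subgroups and the PPS repeats. It is therefore not the total number of between-arm comparisons.

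**The case against.** The best defence is that the reply in 7.6.3.5 answers the usual question correctly. There is one primary endpoint, one analysis labelled primary, two arms and, by SAP 7.6.3.3, no interim analysis. A reader might infer that the trial's primary type I error is inflated. The documents do not support that, and this part of the defence stands in full.

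Second, no section attaches a success criterion to a secondary or subgroup P value, and Protocol 5.4.1.2 justifies most of the secondary endpoints as showing efficacy from several angles. A reader might infer that the plan directs the sponsor to report visit-level or band-level results as established effects. It does not. It only leaves that reading open, because 7.1.3 covers all tests and nothing marks these as nominal.

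Third, a reader might go from an expectation of 25 to near-certainty of at least one false finding. That step does not follow. The P values share subjects across visits, pair changes with percent changes, nest bands within the FAS and use overlapping composites. A familywise rate computed as if they were independent would be misleading, and the documents give no correlations from which to compute a proper one.

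Fourth, a global null is unrealistic for this drug on the protocol's own account. This stands, and it is why the reduced figure of about 12 is given beside 25.

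Finally, naming 7.6.1.1 as the only comparison for a significance claim gives it a status that the visible text does not state, and parts of both documents are blacked out. The sponsor must therefore confirm it. It is nevertheless the analysis that both documents label primary.

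**Conclusion.** The concern holds as a gap in the secondary and subgroup analyses, not as a flaw in the primary one. About 505 between-arm P values fall under a blanket 5% level with no order and no nominal label. About 25 would be expected below 0.05 if the drug had no effect on anything. About 12 would be expected among the 234 on measures for which the documents do not clearly predict an effect, if there were none.

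These figures assume that every scheduled visit yields a contrast and every model can be fitted. They are expectations only: strong correlation means the realised number could be far lower or far higher. The point deserves a change because it is cheap and settles what the trial may claim. It does not threaten the primary conclusion.

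**What to change.** Replace the reply in SAP 7.6.3.5 with a statement to this effect: the FAS risk difference in 7.6.1.1 is the only comparison on which a claim of statistical significance will rest; all other P values (7.6.2.2, 7.6.2.3, 7.6.2.4 and 7.6.3.8) are nominal, unadjusted for multiplicity, and will not be described as statistically significant. Limit the 5% level in 7.1.3 to match.

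Showing full-FAS repeated-measures P values only at Week 104 is optional. It would cut them from 206 to 14 (two in 7.6.2.2, twelve in 7.6.2.3), but it removes no comparison, since a 95% interval at the other visits carries much the same information.

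The cost is two edits to SAP wording, with no change to data, design or patient care. The real price is that the sponsor gives up calling any secondary or eGFR-band result significant.

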7.6.3.6. Comparisons of Subject “Efficacy Assessment Subgroups”

The analyses described in “7.6.1.1 Primary analysis,” “7.6.1.2 Secondary analyses,” “7.6.1.3 Other analysis 1,” “7.6.1.4 Other analysis 2,” and “7.6.2.1 Proportion of subjects with a 40% decline in the eGFR” will be performed, using the PPS as the analysis population.

7.6.3.7. Active-Control Studies Intended to Show Equivalence

Not applicable

7.6.3.8. Analyses of Subgroups

The following subgroup analyses will be performed for the analysis described in 7.6.1.1.

Analysis population(s): FAS

Subgroups: Sex (male, female), age (< 65 years, \geq 65 years), disease duration of type2 diabetes (< median in years, \geq median in years), BMI (< 30, \geq 30), HbA1c on the first day of the treatment period (< 8, \geq 8), eGFR on the first day of the run-in period (\geq 30 and < 45, \geq 45

and < 60 , ≥ 60 and < 90), mean of the eGFR on the first day of the run-in period and that on the first day of the treatment period (< 45 , ≥ 45 and < 60 , ≥ 60), urine ACR on the first day of the treatment period (≤ 1000 , > 1000), systolic blood pressure on the first day of the treatment period (\leq median value, $>$ median value)

Analysis parameter(s): Proportions of subjects with declines of 30% and 40% in the eGFR at Week 104 of the treatment period

Analysis method:

In accordance with “6.2.2. Tabulation of the eGFR at Each Assessment Time Point When Imputing Data Outside the Allowable Time Window,” a dataset will be prepared using [REDACTED] by subgroup. The estimates and variances for this dataset will be combined using Rubin’s rule, and the proportions of subjects with declines of 30% and 40% in the eGFR at Week 104 of the treatment period, the point estimates for the differences between the groups (placebo group minus TA-7284 group), and the 95% confidence intervals based on the Farrington-Manning method, will be calculated for each treatment group. These figures, along with the numbers and proportions of subjects in each of these subgroups, will be presented in forest plots.

The following subgroup analyses will be performed for the analysis described in 7.6.2.2 and 7.6.2.3.

Analysis population(s): FAS

Subgroups: eGFR on the first day of the run-in period (≥ 30 and < 45 , ≥ 45 and < 60 , ≥ 60 and < 90)

Analysis parameter(s): Urine ACR (first morning void urine), eGFR, HbA1c, blood pressure (systolic blood pressure, diastolic blood pressure)

Analysis method:

Urine ACR (First Morning Void Urine)

For the data described in “6.2.4. Tabulation of the Urine ACR Endpoints at Each Assessment Time Point,” for the urine ACR (first morning void urine) at each assessment time point in each group, the geometric mean and 95% confidence interval at the start of the treatment period and up through follow-up (Week 108) will be presented. For each treatment group, time profiles will be prepared showing the geometric mean and 95% confidence interval thereof along the y-axis and each measurement time point up through Week 104 along the x-axis. In addition, for the log-transformed values of the urine ACR (first morning void urine) for each treatment group, the mean change and 95% confidence interval at each assessment time point from Week 4 through follow-up (Week 108) will be calculated. These values will be inverse transformed, and the geometric mean and 95% confidence interval of the ratio for urine ACR (first morning void urine) will be presented.

For the data in “6.2.4. Tabulation of the Urine ACR Endpoints at Each Assessment Time Point,” the mean change at each assessment time point from Week 4 to Week 104 in the log-transformed values of the urine ACR (first morning void urine) will be analyzed in a mixed model for repeated measures using a restricted maximum likelihood (REML) approach, with treatment group, assessment time point,

treatment group—assessment time point interaction, log-transformed value of the urine ACR (first morning void urine) on the first day of the treatment period, and interaction between the assessment time point and the log-transformed value of the urine ACR (first morning void urine) on the first day of the treatment period as covariates. For each treatment group at each assessment time point, the LS mean and standard error, 95% confidence interval, difference between the groups (the TA-7284 group minus the placebo group) in the LS mean, and the standard error and 95% confidence interval thereof, will be calculated. Additionally, the LS means and 95% confidence intervals of the changes in the log-transformed values will be back-transformed, and the geometric LS means and 95% confidence intervals of the ratios of the urine ACR (first morning void urine) will be presented. The values obtained from the following formula will be presented as the percent change from baseline: (geometric LS mean of the ratio of urine ACR [first morning void urine] – 1) x 100. Also, the differences between the groups (the TA-7284 group minus the placebo group) in the LS means, and the 95% confidence intervals thereof, will be back-transformed, and the ratios of the geometric LS means of the ratios of the urine ACR (first morning void urine) and the 95% confidence intervals and P values, will be presented. The percent changes relative to placebo [(ratio of the geometric LS means of the ratio of urine ACR (first morning void urine) – 1) x 100] will also be presented.

The Kenward-Roger method will be used to adjust the degrees of freedom, and an unstructured covariance structure will be used for within-subject error modeling.

However, in within-subject error modeling, if the model fails to converge when using an unstructured covariance matrix, the covariance matrix will be changed according to the following procedure, and the first covariance matrix with successful convergence will be used to perform the analysis.

Heterogeneous Toeplitz (TOEPH) → Heterogeneous AR(1) (ARH(1)) → Heterogeneous CS (CSH)
→ Toeplitz (TOEP) → First-order autoregressive (AR(1)) → Compound symmetry (CS)

eGFR, HbA1c, blood pressure (systolic blood pressure, diastolic blood pressure)

For the data in “6.2.1. Tabulation by eGFR Assessment Time Point” and “6.2.3. Tabulation of Endpoints Other Than the eGFR and Urine ACR at Each Assessment Time Point,” for each treatment group, descriptive statistics will be provided for the values of each assessment parameter both on the first day of the treatment period (for the eGFR, this will be the mean of the value obtained on the first day of the run-in period and the value obtained on the first day of the treatment period) and at each of the assessment time points until follow-up (Week 108) (Week 104 for the parameter of blood pressure). For each treatment group, the mean change and standard deviation at each assessment time point from the first day of the treatment period (for the eGFR, the mean of the value on the first day of the run-in period and the value on the first day of the treatment period) until follow-up (Week 108) (Week 104 for the parameter of blood pressure) will be calculated for each of the eGFR, HbA1c, and blood pressure

(systolic blood pressure, diastolic blood pressure). In addition, the mean percent changes (and standard deviations) from the mean of the eGFR value on the first day of the run-in period and that on the first day of the treatment period to each assessment time point through follow-up (Week 108) will be calculated for each treatment group.

For the data in “6.2.1. Tabulation by eGFR Assessment Time Point” and “6.2.3. Tabulation of Endpoints Other Than the eGFR and Urine ACR at Each Assessment Time Point,” each of the mean changes at each assessment time point from Week 4 to Week 104 in the eGFR, HbA1c, and blood pressure (systolic blood pressure, diastolic blood pressure), and each of the mean percent changes at each assessment time point from Week 4 to Week 104 in the eGFR will be analyzed in a mixed model for repeated measures using a restricted maximum likelihood (REML) approach, with treatment group, assessment time point, treatment group—assessment time point interaction as factors, and the values of the assessment parameters on the first day of the treatment period and the interactions between the assessment time points and the values of the assessment parameters on the first day of the treatment period as covariates. The LS means and standard errors at each measurement time point for each treatment group will be presented. The differences between the groups in the LS mean (the TA-7284 group minus the placebo group) and the 95% confidence intervals and P values will also be presented. In addition, time profiles will be prepared for each treatment group for each of the mean change and the mean percent change, with the LS means and standard errors, calculated based on MMRM, along the y-axis and each measurement time point up through Week 104 along the x-axis, for the eGFR.

The Kenward-Roger method will be used to adjust the degrees of freedom, and an unstructured covariance structure will be used for within-subject error modeling.

However, in within-subject error modeling, if the model fails to converge when using an unstructured covariance matrix, the covariance matrix will be changed according to the following procedure, and the first covariance matrix with successful convergence will be used to perform the analysis.

Heterogeneous Toeplitz (TOEPH) → Heterogeneous AR(1) (ARH(1)) → Heterogeneous CS (CSH) → Toeplitz (TOEP) → First-order autoregressive (AR(1)) → Compound symmetry (CS)

